6.1 Antitumor Effect – Solid Tumors

For the purposes of this study, patients' disease should be evaluated according to the schedule in Section [7](#). If a patient's disease responds, a confirmatory scan must be performed at least 4 weeks following initial documentation of objective response.

Response and progression will be evaluated in this study using the international criteria proposed by the revised Response Evaluation Criteria in Solid Tumors (RECIST) guideline (version 1.1) [*Eur J Ca* 45:228-247, 2009]. Changes in the largest diameter (unidimensional measurement) of the tumor lesions and the shortest diameter in the case of malignant lymph nodes are used in RECIST.

The following general principles must be followed:

1. To assess objective response, it is necessary to estimate the overall tumor burden at baseline to which subsequent measurements will be compared. All baseline evaluations should be performed as closely as possible to the beginning of treatment and **never more than four weeks** before registration.
2. Measurable disease is defined by the presence of at least one measurable lesion.
3. All measurements should be recorded in metric notation by use of a ruler or calipers.
4. The same method of assessment and the same technique must be used to characterize each identified lesion at baseline and during follow-up.

6.1.1 Definitions

Evaluable for Objective Response

Only those patients who have measurable disease present at baseline, have received at least one cycle of therapy, and have had their disease re-evaluated will be considered evaluable for response. These patients will have their response classified according to the definitions stated below. (Note: Patients who exhibit objective disease progression prior to the end of cycle 1 will also be considered evaluable.)

Evaluable Non-Target Disease Response

Patients who have lesions present at baseline that are evaluable but do not meet the definitions of measurable disease, have received at least one cycle of therapy, and have had their disease re-evaluated will be considered evaluable for non-target lesion assessment. The response assessment is based on the presence, absence, or unequivocal progression of the lesions.

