5.1 Administration Schedule

1 cycle = 28 days

Open label tamoxifen 20 mg PO (single dose) daily until progression, unacceptable toxicities, or any other condition outlined in Section [5.5](#).

Rev. 5/14

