6.1.4.4 Evaluation of Best Overall Response

The best overall response is the best response recorded from the start of the treatment until disease progression/recurrence or non-protocol therapy (taking as reference for progressive disease the smallest measurements recorded since the treatment started). The patient's best response assignment will depend on the achievement of both measurement and confirmation criteria.

For Patients with Measurable Disease (i.e., Target Disease)

Target Lesions	Non-Target Lesions	New Lesions*	Best Overall Response	Remarks
CR	CR	No	CR	
CR	Non-CR/Non-PD***	No	PR	
CR	Not evaluated	No	PR	
PR	Non-PD***/not evaluated	No	PR	
SD	Non-PD***/not evaluated	No	SD	Documented at least once \geq 12 wks. from study entry
PD	Any	Yes or No	PD	No prior SD, PR or CR
Any	PD**	Yes or No	PD***	
Any	Any	Yes	PD	

* See RECIST 1.1 manuscript for further details on what is evidence of a new lesion.

** In exceptional circumstances, unequivocal progression in non-target lesions may be accepted as disease progression.

***PD in non-target lesions should not normally trump target lesion status. It must be representative of overall disease status change, not a single lesion increase. Please refer to the Evaluation of Non-Target Lesions-Progressive Disease section for further explanation.

NOTE: Patients with a global deterioration of health status requiring discontinuation of treatment without objective evidence of disease progression at that time should be reported as "*symptomatic deterioration*." Every effort should be made to document the objective progression even after discontinuation of treatment.

For Patients with Only Non-Measurable Disease (i.e., Non-Target Disease)

Non-Target Lesions	New Lesions	Overall Response
CR	No	CR
Non-CR/non-PD	No	Non-CR/non-PD*
Not all evaluated	No	not evaluated
Unequivocal PD	Yes or No	PD
Any	Yes	PD

* 'Non-CR/non-PD' is preferred over 'stable disease' for non-target disease since SD is increasingly used as an endpoint for assessment of efficacy in some trials so to assign this category when no lesions can be measured is not advised

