7.1 Therapeutic Parameters

1. Prestudy scans and x-rays used to assess all measurable or non-measurable sites of disease must be done within **4 weeks** prior to registration.
2. Prestudy CBC (with differential and platelet count) should be done \leq **4 weeks** prior to registration.
3. All required prestudy chemistries, as outlined in Section [3](#), should be done \leq **4 weeks** prior to registration.

NOTE: 1 cycle = 28 days

	Pre-Study		End of Cycles 1 and 2 ⁹	End of Cycle 3 ⁹	Every 3 cycles (after cycle 3) ⁹	At discontinuation of treatment ¹⁰	Post treatment up to 5 years from study entry
	\leq 4 weeks prior to registration	\leq 2 weeks prior to registration					
Height	X						
History, Physical Exam, ECOG PS, Vital signs, Weight	X		X	X	X	X	X ³
Concomitant Medications	X		X	X	X		X ⁸
CBC ¹	X			X	X	X	
Bilirubin, SGOT (AST), SGPT (ALT)	X			X	X	X	
Lipid profile ¹¹	X			X			
HCG ²		X					
Bone scan	X ⁶			X ⁶	X ⁶		X ^{6,8}
Tumor assessment by PE	X			X	X	X	X ⁸
Tumor assessment by CT or MRI ⁷	X			X	X	X	X ⁸
Research blood submissions ⁵	X ⁴			X		X	

- Rev. 8/12
1. CBCs (with differential and platelet count) which includes WBC, ANC, Platelets, Hgb, and Hct.
 2. All females of child-bearing potential must have a blood or urine test within 2 weeks prior to registration to rule out pregnancy.
 3. Every 3 months if patient is $<$ 2 years from study entry, every 6 months if patient is 2-5 years from study entry. No specific requirements if patient is more than 5 years from study entry.
- Rev. 5/11

- Rev. 8/12 4. It is strongly encouraged that the whole blood collected for the genotype verification is collected prior to protocol treatment, but may be collected at the end of cycle three (3) if unable to collect at baseline.
- Rev. 8/12 5. Refer to Sections [7.2](#) and [11](#) for submission instructions.
- Rev. 5/11, 6. Baseline bone scan required in all patients; repeat in follow-up as clinically indicated.
- 8/12 **NOTE:** If bone scan done within 6 months prior to registration showed no evidence suggesting bone metastases and no clinical indication of skeletal pain or other evidence suggesting bone metastases, a repeat baseline bone scan is not required.
- Rev. 5/11, 7. CT or MRI of chest/abdomen/pelvis are required at baseline. Those tests required to follow known site(s) of disease should be repeated at the end of Cycle 3 and then every 3 cycles during treatment and according to the follow up schedule if off treatment, until first progression of disease.

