- NOTE: If CT or MRI of chest and/or abdomen/pelvis done within 6 months prior to registration showed no evidence of disease in the area(s) and no clinical indication suggesting new metastases, full re-staging including all areas is not required; however, ensure that disease is evaluable per RECIST requirements (Section [6](#)).
- Rev. 5/11 8. Concomitant medication and tumor assessments are to be done up to (and including) the assessment which shows first progression of disease. If patient discontinues treatment due to reasons other than disease progression, concomitant medication and tumor assessments should be performed until disease progression on the following schedule: Every 3 months if patient is < 2 years from study entry, every 6 months if patient is 2-5 years from study entry. No specific requirements if patient is more than 5 years from study entry.
- Rev. 5/11 9. All tests should be performed at the end of the cycle. A +/- 7 day window will be allowed in case of scheduling problems.
- Rev. 5/11 10. Repeat any test not done within the prior 28 days.
- Rev. 5/11 11. Lipid profile should be fasting.

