Due to the disproportionate expected percentage of poor vs. intermediate and extensive metabolizers, Cox proportional hazards models will be used to estimate the effect of CYP2D6 score with respect to PFS while adjusting for possible confounding factors such as prior AI use and other biomarkers that are being assessed in this study, to assess the

effect of prior AI use and other biomarkers alone with respect to PFS, and to test for interactions between the various baseline factors with respect to PFS.

Due to the low estimated percentage of patients with a CYP2D6 score =0, a stopping rule is incorporated into this design. If the rate of accrual of poor metabolizers is less than 8% or less than 1 patient with a CYP2D6 score=0 per month in the first 18 months that the study is open, the study will be suspended for further evaluation of feasibility.

The distribution of progression-free survival for the patients with a CYP2D6 score=0, 1, and 2 will be estimated using the Kaplan Meier method. Best overall response rate will be summarized as a proportion overall and within patients with a CYP2D6 score=0 vs. 1+2 and within score=0, 1, and 2. Proportion progression-free at 6 months will be summarized overall and within patients with CYP2D6 score=0 vs. 1+2, and within score=0, 1, and 2. Endoxifen levels will be summarized descriptively overall and within responders and non-responders. Comparisons between responders and non-responders with respect to endoxifen levels will be explored using a Wilcoxon rank sum test.

Safety Monitoring

Interim analyses of toxicity are performed twice yearly for all ECOG-ACRIN studies. Reports of these analyses are sent to the ECOG-ACRIN Principal Investigator or Senior Investigator at the participating institutions. Expedited reporting of certain adverse events is required, as described in Section [5.2](#).

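### The only response set defined drops treated patients who are never re-evaluated, and most who stop within cycle 1, instead of counting them as non-responders; Section 9 names no other denominator

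*Combined protocol and SAP*

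**What the plan says.** - **Response set (Section 6.1.1).** Only patients with measurable disease at baseline who "have received at least one cycle of therapy, and have had their disease re-evaluated will be considered evaluable for response" are included. A note adds one exception: "Patients who exhibit objective disease progression prior to the end of cycle 1 will also be considered evaluable".
- **Timing (Sections 5.1 and 7.1).** With "1 cycle = 28 days", imaging of known disease "should be repeated at the end of Cycle 3 and then every 3 cycles during treatment". The first scheduled tumor assessment is therefore day 84, and "A +/- 7 day window will be allowed in case of scheduling problems". None is scheduled at the end of cycles 1 and 2.
- **Leaving treatment (Section 7.1).** The schedule also marks tumor assessment by physical exam and by CT or MRI in the column headed "At discontinuation of treatment", for any test not done in the previous 28 days. After stopping for a reason other than progression, assessments continue every 3 months in the first 2 years, until progression.
- **Clinical failure (Section 6.1.4.4).** "Patients with a global deterioration of health status requiring discontinuation of treatment without objective evidence of disease progression at that time" are reported as symptomatic deterioration. Sites are asked to document objective progression afterwards, but neither response table places these patients among the non-responders.
- **Analysis (Section 9).** "Best overall response rate will be summarized as a proportion overall" and by CYP2D6 score. No denominator is named, and nothing is said about patients without an assessment.

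**The concern.** A patient with no re-evaluation has no recorded response. Leaving that patient out of the denominator keeps the numerator the same and raises the rate. Whether a patient goes unassessed is likely to depend on outcome, because death and rapid decline prevent a scan. The trial's own hypothesis is that score 0 fails sooner, so the loss may differ between the groups being compared.

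Two secondary objectives are at stake: 2.2.4 (CYP2D6 score and response) and, to a lesser degree, 2.2.3 (endoxifen and response). Because Section 9 is silent, the exclusive wording of 6.1.1 is the natural default for whoever programs the analysis.

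**Working it through.** **1. Who stays and who leaves (patients with measurable disease)**

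| Situation | In the 6.1.1 set? |
|---|---|
| Objective progression before the end of cycle 1 | Yes, by the note |
| At least one cycle, stops before week 12, assessed at discontinuation or later | Yes |
| At least one cycle, then dies, withdraws, is lost or deteriorates with no assessment | No |
| Stops within cycle 1 without objective progression by its end, scanned or not | No |

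**2. What the plan's figures imply about early failure**

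The plan states no rate, power or sample size for response. Its hazard-ratio table can be reproduced, and this gives an implied speed of failure.

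Inputs from Section 9: 204 scored patients, 180 progressed, 24 months of accrual, at least 3 months of follow-up, 10% score 0, HR 1.95, two-sided 5%, 80% power. Assumed here: exponential PFS, uniform accrual, analysis 3 months after the last entry.

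- P(event) = 1 − [exp(−3λ) − exp(−27λ)]/(24λ).
- Solving 0.9·P(λ) + 0.1·P(1.95λ) = 180/204 gives λ = 0.1863 per month in scores 1-2, a median of ln 2/0.1863 = 3.7 months (1.9 in score 0).
- Expected events: 160.4 in scores 1-2 and 19.6 in score 0.
- Detectable HR = exp[(1.960 + 0.842) × √(1/19.6 + 1/160.4)] = 1.955, against 1.95 stated. The same steps at 8% and 12% prevalence give 2.09 and 1.86, as stated.

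Day 84 is 84/30.44 = 2.76 months. The probability of a PFS event by then is:

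- scores 1-2: 1 − exp(−0.1863 × 2.76) = 0.402;
- score 0: 1 − exp(−1.95 × 0.1863 × 2.76) = 0.633.

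These are ceilings on the loss through early failure, not estimates of it, since assessments at discontinuation keep many of these patients in.

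**3. Inflation of the rate**

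Let u be the share of pre-week-12 failures never re-evaluated (assumed). The dropped share is d = u × P(event by day 84), and the evaluable-set rate is the all-treated rate divided by (1 − d). The 9-month median is an assumed alternative to the implied 3.7 months.

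| Median PFS, scores 1-2 (months) | u | d, scores 1-2 | d, score 0 | Factor, scores 1-2 | Factor, score 0 |
|---|---|---|---|---|---|
| 3.7 | 10% | 4.0% | 6.3% | 1.04 | 1.07 |
| 3.7 | 25% | 10.1% | 15.8% | 1.11 | 1.19 |
| 3.7 | 50% | 20.1% | 31.7% | 1.25 | 1.46 |
| 9 | 25% | 4.8% | 8.5% | 1.05 | 1.09 |

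**4. Effect on the contrast**

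At u = 25% the ratio of score 0 to scores 1-2 is multiplied by 1.188/1.112 = 1.07 (median 3.7 months) or 1.093/1.050 = 1.04 (median 9 months). The effect on the difference depends on the true rates. With u = 25%, median 3.7 months and assumed true rates:

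| True rates, scores 1-2 / score 0 | Evaluable-set rates | Difference, points (scores 1-2 minus score 0) | Ratio |
|---|---|---|---|
| 20% / 10% | 22.2% / 11.9% | 10.0 → 10.4 | 0.50 → 0.53 |
| 20% / 15% | 22.2% / 17.8% | 5.0 → 4.4 | 0.75 → 0.80 |
| 20% / 20% | 22.2% / 23.8% | 0 → −1.5 | 1.00 → 1.07 |

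The overstatement in points is p × d/(1 − d). It is larger in score 0 only if the true ratio exceeds 0.1117/0.1880 = 0.59. That threshold is 0.54 to 0.62 for u from 50% to 10% at this median.

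**The case against.** The best defense is the schedule. A reader who sees a first scan at week 12 might infer that early clinical failures in general leave the denominator. The documents do not support that. A patient who stops in cycle 2 or 3 is due an assessment at discontinuation and others every 3 months, and sites must try to document progression. Once assessed, that patient is evaluable. Re-evaluation need not be imaging either, since Section 6.1.3 accepts caliper measurement of superficial lesions. This stands and limits the loss. It does not remove it: a patient who has died or withdrawn cannot be scanned, and a scan does not readmit someone who stopped within cycle 1 without objective progression.

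Second, Section 9 never adopts the 6.1.1 set. That is true, so the defect is as much an unstated denominator as a biased one. One sentence cures both.

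Third, score 0 is only about 20 patients (10% of 204), fewer with measurable disease. At d = 15.8% about 3 would drop out (20.4 × 0.158 = 3.2), a shift that is small beside sampling error. This also stands, but it is no reason to leave the rule open until the data are seen.

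Fourth, plasma is taken only at the end of cycle 3 and off treatment (Section 11.2). A patient who reaches neither draw has no endoxifen value under any denominator, so a new rule helps objective 2.2.3 little.

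**Conclusion.** The point holds for a defined group: treated patients with measurable disease who are never re-evaluated, and those who stop within cycle 1 without objective progression. Dropping the first kind can only raise the reported rate. Dropping the second raises it too, unless such a patient later shows a confirmed response.

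With a quarter of pre-week-12 failures unassessed, the inflation is about 1.05-1.11 in scores 1-2 and 1.09-1.19 in score 0. This rests on the assumed unassessed share (taken as equal in both groups), exponential PFS, and a median between the implied 3.7 months and an assumed 9. The share with measurable disease is not given either.

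A reader might infer that the overstatement is always greatest in score 0 and that the contrast is always attenuated. The first is true of relative inflation at an equal missed-assessment share, but not always in percentage points. The second is true of the ratio when score 0 responds less often; the difference can widen or narrow.

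Response is secondary and the by-score summary is descriptive. The primary PFS comparison does not use this set. The change should be made, but the main result does not depend on it.

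**What to change.** In Section 9:

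- Report best overall response in all eligible, treated patients with measurable disease at baseline. Count those with no post-baseline assessment as non-responders, and classify patients who stopped within cycle 1 by the best response recorded under 6.1.4.4.
- Require a CYP2D6 score only for the by-score summaries, not for the overall rate.
- Report the 6.1.1 evaluable set as a sensitivity analysis, with the number excluded, by score and reason.
- For objective 2.2.3, state how many patients have no endoxifen value.

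The cost is wording only, with no added patients, visits or scans. The reported response rate will be slightly lower, and the gain for objective 2.2.3 is limited by the plasma schedule.

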6.1.2 Disease Parameters

Measurable Disease

Measurable lesions are defined as those that can be accurately measured in at least one dimension (longest diameter to be recorded)

as \geq 20 mm by chest x-ray, as \geq 10 mm with CT scan, or \geq 10 mm with calipers by clinical exam. All tumor measurements must be recorded in millimeters.

NOTE: Tumor lesions that are situated in a previously irradiated area are not considered measurable.

Malignant Lymph Nodes

To be considered pathologically enlarged and measurable, a lymph node must be \geq 15 mm in **short** axis when assessed by CT scan (CT scan slice thickness recommended to be no greater than 5 mm). At baseline and in follow-up, only the **short** axis will be measured and followed.

Non-measurable Disease

All other lesions (or sites of disease), including small lesions (longest diameter $<$ 10 mm or pathological lymph nodes with \geq 10 to $<$ 15 mm short axis), are considered non-measurable disease. Bone lesions, leptomeningeal disease, ascites, pleural/pericardial effusions, lymphangitis cutis/pulmonitis, inflammatory breast disease, and abdominal masses (not followed by CT or MRI), are considered as non-measurable. Non-measurable also includes lesions that are $<$ 20 mm by chest x-ray.

NOTE: Cystic lesions that meet the criteria for radiographically defined simple cysts should not be considered as malignant lesions (neither measurable nor non-measurable) since they are, by definition, simple cysts.

'Cystic lesions' thought to represent cystic metastases can be considered as measurable lesions, if they meet the definition of measurability described above. However, if non-cystic lesions are present in the same patient, these are preferred for selection as target lesions.

Target Lesions

All measurable lesions up to a maximum of 2 lesions per organ and 5 lesions in total, representative of all involved organs, should be identified as **target lesions** and recorded and measured at baseline. Target lesions should be selected on the basis of their size (lesions with the longest diameter), be representative of all involved organs, but in addition should be those that lend themselves to reproducible repeated measurements. It may be the case that, on occasion, the largest lesion does not lend itself to reproducible measurement in which circumstance the next largest lesion which can be measured reproducibly should be selected.

A sum of the diameters (longest for non-nodal lesions, short axis for nodal lesions) for all target lesions will be calculated and reported as the baseline sum diameters. If lymph nodes are to be included in the sum, then only the short axis is added into the sum. The baseline sum of the diameters will be used as reference to further characterize any

objective tumor regression in the measurable dimension of the disease.

Non-target Lesions

All other lesions (or sites of disease) including any measurable lesions over and above the 5 target lesions should be identified as **non-target lesions** and should also be recorded at baseline. Measurements of these lesions are not required, but the presence or absence of unequivocal progression of each should be noted throughout follow-up.

6.1.3 Methods for Evaluation of Measurable Disease

All measurements should be taken and recorded in metric notation using a ruler or calipers. All baseline evaluations should be performed as closely as possible to the beginning of treatment and never more than 4 weeks before registration.

The same method of assessment and the same technique must be used to characterize each identified and reported lesion at baseline and during follow-up. Imaging-based evaluation is preferred to evaluation by clinical examination unless the lesion(s) being followed cannot be imaged but are assessable by clinical exam.

Clinical Lesions

Clinical lesions will only be considered measurable when they are superficial (e.g., skin nodules and palpable lymph nodes) and ≥ 10 mm in diameter as assessed using calipers (e.g., skin nodules). In the case of skin lesions, documentation by color photography, including a ruler to estimate the size of the lesion, is recommended.

Chest X-ray

Lesions on chest x-ray are acceptable as measurable lesions when they are clearly defined and surrounded by aerated lung. However, CT is preferable.

Conventional CT and MRI

This guideline has defined measurability of lesions on CT scan based on the assumption that CT slice thickness is 5 mm or less. If CT scans have slice thickness greater than 5 mm, the minimum size for a measurable lesion should be twice the slice thickness. MRI is also acceptable in certain situations (e.g. for body scans).

Use of MRI remains a complex issue. MRI has excellent contrast, spatial, and temporal resolution; however, there are many image acquisition variables involved in MRI which greatly impact image quality, lesion conspicuity, and measurement. Furthermore, the availability of MRI is variable globally. As with CT, if an MRI is performed, the technical specifications of the scanning sequences used should be optimized for the evaluation of the type and site of disease. Furthermore, as with CT, the modality used at follow-up must be the same as was used at baseline and the lesions should be measured/assessed on the same pulse sequence. It is beyond the

scope of the RECIST guidelines to prescribe specific MRI pulse sequence parameters for all scanners, body parts, and diseases. Ideally, the same type of scanner should be used and the image acquisition protocol should be followed as closely as possible to prior scans. Body scans should be performed with breath-hold scanning techniques, if possible.

PET-CT

At present, the low dose or attenuation correction CT portion of a combined PET-CT is not always of optimal diagnostic CT quality for use with RECIST measurements. However, if the site can document that the CT performed as part of a PET-CT is of identical diagnostic quality to a diagnostic CT (with IV and oral contrast), then the CT portion of the PET-CT can be used for RECIST measurements and can be used interchangeably with conventional CT in accurately measuring cancer lesions over time. Note, however, that the PET portion of the CT introduces additional data which may bias an investigator if it is not routinely or serially performed.

Ultrasound

Ultrasound is not useful in assessment of lesion size and should not be used as a method of measurement. Ultrasound examinations cannot be reproduced in their entirety for independent review at a later date and, because they are operator dependent, it cannot be guaranteed that the same technique and measurements will be taken from one assessment to the next. If new lesions are identified by ultrasound in the course of the study, confirmation by CT or MRI is advised. If there is concern about radiation exposure at CT, MRI may be used instead of CT in selected instances.

Endoscopy, Laparoscopy

The utilization of these techniques for objective tumor evaluation is not advised. However, such techniques may be useful to confirm complete pathological response when biopsies are obtained or to determine relapse in trials where recurrence following complete response (CR) or surgical resection is an endpoint.

Tumor Markers

Tumor markers alone cannot be used to assess response. If markers are initially above the upper normal limit, they must normalize for a patient to be considered in complete clinical response. Specific guidelines for both CA-125 response (in recurrent ovarian cancer) and PSA response (in recurrent prostate cancer) have been published [JNCI 96:487-488, 2004; J Clin Oncol 17, 3461-3467, 1999; J Clin Oncol 26:1148-1159, 2008]. In addition, the Gynecologic Cancer Intergroup has developed CA-125 progression criteria which are to be integrated with objective tumor assessment for use in first-line trials in ovarian cancer [JNCI 92:1534-1535, 2000].

Cytology, Histology

These techniques can be used to differentiate between partial responses (PR) and complete responses (CR) in rare cases (e.g., residual lesions in tumor types, such as germ cell tumors, where known residual benign tumors can remain).

The cytological confirmation of the neoplastic origin of any effusion that appears or worsens during treatment when the measurable tumor has met criteria for response or stable disease is mandatory to differentiate between response or stable disease (an effusion may be a side effect of the treatment) and progressive disease.

